9.4.3 ANALYSIS OF THE SECONDARY ENDPOINT(S)

The secondary endpoints are ICU admission or death and invasive ventilation or death within 21 days after randomization, as established by medical record review. Outcomes of subjects who withdraw

consent or are otherwise lost to follow-up before 21 days will be considered missing. The intention to treat population for each endpoint will be used for analysis. Estimation and testing procedures will follow those of the primary efficacy endpoint.

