1 PROTOCOL SUMMARY

1.1 SYNOPSIS			
Title:	RANDOMIZED DOUBLE-BLIND PLACEBO-CONTROLLED PROOF-OF-CONCEPT TRIAL OF RESVERATROL FOR THE OUTPATIENT TREATMENT OF MILD CORONAVIRUS DISEASE (COVID-19)		
Study Description:	•	trial to determine the safety and explore the efficacy of using itamin D3 to treat patients with mild COVID-19	
Objectives:	Primary Objective:	To compare the 21-day hospitalization rate among early or mild stage COVID-19 patients taking a 15-day regimen of resveratrol pus vitamin D3 to that for patients taking an identical placebo regimen.	
	Secondary Objectives:	Decrease morbidity and mortality in terms of reduced days of symptoms, reduced rate of ICU admission, reduced rate of mechanical ventilation, and reduced mortality.	
Endpoints:	Primary Endpoint:	Hospitalization rate	
	Secondary Endpoints:	ICU Admission rate, invasive ventilation rates, duration of symptoms, and mortality rates.	
Study Population:	200 hundred patients (100 per group) 45 years and older who test positive for SARS- COV2 who have mild COVID-19 based on WHO Baseline Severity Categorization		
Phase:	2		
Description of Sites/Facilities Enrolling Participants:	Outpatients presenting to COVID-19 testing sites of Mt Carmel Health Systems in Columbus, OH, which may include drive-thru testing centers, emergency departments, urgent care centers.		
Description of Study Intervention:	Patients will be placed on a 15-day course of two 500 mg resveratrol capsules 4 times per day, versus the same dosing frequency of placebo. Both groups will receive 100,000 IU on day one only.		
Study Duration	: up to 6 months		
Participant Duration:	60 days		

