9.2 SAMPLE SIZE DETERMINATION

[figure not shown]
The maximum total number of randomized subjects is capped at 200 by FDA request. We present power analyses of the primary outcome measure (hospitalization) assuming multiple placebo arm

hospitalization rates and effect sizes, as well as for secondary outcome measures. No interim analyses for efficacy are planned, and none are included in the following power calculations.

The primary outcome measure is hospitalization within 21 days of randomization. We provide conservative power estimates by assuming a binary outcome with 5% non-informative loss to follow-up before 21 days. We anticipate this relatively low rate of loss because the endpoint is designed to be evaluable by chart review unless the subject withdraws consent. Hypotheses are as specified in the previous section, and the Z statistic for a two-proportion test is used. The primary Kaplan-Meier analysis will yield slightly better power by treating the outcomes of patients lost to follow-up as censored at the time of last follow-up.

The rate of hospitalization among confirmed cases of COVID-19 ranges between 21% in the 45-54 age bracket, up to 31% for patient's >85 (CDC, 2020). We assumed a mid-point hospitalization rate of 25% for the initial sample size calculation. To achieve 80% power at the 5% two-sided significance level with complete follow-up on 95 subjects per arm with two-sample proportion test, we require a 10% or lower hospitalization rate in the resveratrol arm, compared to a 25% rate in the placebo arm (estimated by power.prop.test, R statistical software). This corresponds to an odds ratio of 1 / 3.

The required resveratrol arm event rate for various placebo arm event rates are plotted in Figure 3. This curve applies to the power for all outcome measures, with lower rates of all secondary outcome events expected to be lower in both arms.

95 complete observations per arm, 80% power

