9.4.2 ANALYSIS OF THE PRIMARY EFFICACY ENDPOINT(S)

The primary efficacy endpoint is hospitalization for any cause within 21 days after randomization, as established by medical record review. Outcomes of subjects who withdraw consent or are otherwise lost to follow-up before 21 days will be considered missing. The intention to treat population for the hospitalization endpoint will be used for analysis. A logistic regression model will be fit with age, sex, race, ethnicity, risk group (see Sec 9.4.7), and randomized group as covariates, with the coefficient to randomized group as the primary estimand. Missing outcome data will be imputed using multiple imputation based on predictions from the logistic regression model of the outcome. Sensitivity analyses will include analyses in which patients lost to follow-up are assumed to not have been hospitalized, and tipping-point analyses systematically and comprehensively varying assumptions about missing outcomes on the treatment and placebo arms independently.

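### The secondary endpoints reuse the full maximum-likelihood logistic model on very few expected events, with no rule for an arm without events, where the treatment coefficient is infinite

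*Combined protocol and SAP*

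**What the plan says.** Section 9.4.3 names two secondary endpoints over 21 days, ICU admission or death and invasive ventilation or death. It analyzes them in the intention-to-treat population and adds: "Estimation and testing procedures will follow those of the primary efficacy endpoint".

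The primary procedure is in section 9.4.2: "A logistic regression model will be fit with age, sex, race, ethnicity, risk group" and randomized group. The coefficient for randomized group is the primary estimand. Missing outcomes are multiply imputed from predictions of the same logistic model. Tipping-point analyses appear there as sensitivity analyses.

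Section 9.4.1 gives both secondaries confirmatory status: if the primary is significant, they are tested by Bonferroni-Holm within a 5% familywise error rate.

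Section 9.2 gives no ICU or ventilation rate. It says only that the power curve applies to every outcome, "with lower rates of all secondary outcome events expected to be lower in both arms".

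The plan gives no rule for sparse events, an arm without events, or a model that does not converge. It also does not say whether the treatment coefficient is tested by a Wald or a likelihood-ratio statistic.

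**The concern.** Both secondaries count rarer outcomes than the primary, yet they inherit a model with at least six slopes, more if race has more than two levels. Two things follow.

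- **Too few events for the model.** Maximum-likelihood estimates are unstable and biased away from zero when there are only one or two events per slope.
- **No finite estimate for an empty arm.** If no resveratrol patient has the event, the likelihood keeps rising as the treatment coefficient goes to minus infinity. Software then reports an arbitrary large coefficient with an enormous standard error. This is the most favorable result the resveratrol arm can give, and the estimand the plan names does not exist for it. Under a Wald test, superiority could not be declared.

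Imputation is exposed to the same problem because it uses the same fit. Without a stated rule, the sponsor would choose the method after seeing the data, among p-values that differ greatly.

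**Working it through.** **Inputs from the documents**

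- Size: "The maximum total number of randomized subjects is capped at 200 by FDA request", 100 per group (section 1.1).
- Evaluable patients: 95 per arm, after "5% non-informative loss to follow-up before 21 days" (section 9.2).
- Hospitalization: 25% placebo, 10% resveratrol (section 9.2).
- Model: age, sex, race, ethnicity, risk group and arm, so at least 6 slopes (section 9.4.2).
- Holm over two endpoints, so the first step is at 2.5% (section 9.4.1).

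**Assumption.** A fraction f of hospitalized patients reaches the secondary endpoint, the same in both arms. The documents do not give f; the range shown is 10% to 50%.

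**The plan's own figure.** For 25% versus 10% with 95 per arm, a two-sided 5% two-proportion test has power 0.781. Exactly 80% needs 9.7% on resveratrol, which rounds to the stated 10%. The odds ratio is (0.10/0.90)/(0.25/0.75) = 1/3, as stated. Section 9.2 is therefore reproduced to rounding.

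**Expected events and empty-arm probability**

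- Events = 95 × 0.25f + 95 × 0.10f = 33.25f
- P(no resveratrol event) = (1 − 0.10f)^95

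| f | Rates, placebo / resveratrol | Expected events | Events per slope (6 slopes) | P(no resveratrol event) |
|---|---|---|---|---|
| 10% | 2.5% / 1% | 3.3 | 0.6 | 38.5% |
| 20% | 5% / 2% | 6.7 | 1.1 | 14.7% |
| 30% | 7.5% / 3% | 10.0 | 1.7 | 5.5% |
| 40% | 10% / 4% | 13.3 | 2.2 | 2.1% |
| 50% | 12.5% / 5% | 16.6 | 2.8 | 0.8% |

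If resveratrol hospitalization were 5% instead of 10%, P(no resveratrol event) would be 62%, 38%, 24% and 15% for f = 10% to 40%.

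**Simulation of the adjusted model.** 600 trials per value of f, 7 slopes, assumed covariate mix (race 75/18/7%, ethnicity 5%, risk group 40%). The treatment coefficient was infinite in about 45%, 17%, 6% and 3% of trials for f = 10% to 40%. Among trials with a significant primary, the only ones in which the secondaries are formally tested, the figures were 44%, 19%, 7% and 4%.

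**What each method returns for 0/95 versus 7/95 (unadjusted)**

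| Method | Result |
|---|---|
| Maximum likelihood, Wald | coefficient about −22, SE about 13,400, p = 0.999 |
| Likelihood-ratio test | p = 0.0016, no finite estimate |
| Fisher exact | p = 0.014 |
| Firth, penalized likelihood ratio | odds ratio 0.06, p = 0.006 |

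The Wald p-value is about 0.999 for every count from 0 versus 3 to 0 versus 10.

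**How often a significant result would be lost.** Firth reaches 2.5% with 0 versus 6 (p = 0.012) but not with 0 versus 5 (p = 0.0252). The loss under a Wald test is therefore P(no resveratrol event) × P(at least 6 placebo events). At 5%/2% this is 0.147 × 0.339 = 5.0%. Over f = 10%, 20%, 30%, 40% and 50% it is 1.2%, 5.0%, 4.0%, 1.9% and 0.8%. These figures are not conditional on a significant primary.

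**Imputation.** If imputation draws coefficients from the separated fit by the usual normal approximation, a draw from mean −22 with SE 13,441 is positive with probability Φ(−22/13,441) ≈ 0.499. The roughly 5 missing resveratrol patients would then be imputed as almost certain events in about half the data sets, although no event was observed in that arm.

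**The case against.** The strongest reply is that the plan does not commit itself to a Wald test. A likelihood-ratio test still works with an empty arm and gives p = 0.0016 for 0 versus 7. This stands as far as the p-value goes. It does not supply a finite value for the coefficient that section 9.4.2 makes the estimand. The plan also imputes missing outcomes, and the usual pooling of coefficients and standard errors is a Wald procedure.

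Likewise, imputation from fitted probabilities alone would give a predicted risk near zero for the empty arm, which can be computed. The instability arises only if coefficients are drawn, and section 9.4.2 does not say which is meant.

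A reader might infer more than the documents support in three ways:

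- **That the treatment coefficient fails whatever the event rate.** No ICU or ventilation rate is given. At 40% to 50% progression an empty resveratrol arm has probability of about 2% or less. Only the shortage of events per slope persists over the whole range.
- **That the model fails in nearly every trial.** In the simulation some coefficient was infinite in 73% to 99% of trials, but mostly in small race or ethnicity cells of an assumed mix. That does not by itself make the treatment coefficient infinite.
- **That a high chance of an empty arm means a high chance of losing a finding.** Where an empty arm is likeliest, placebo events are usually too few for any test to reject.

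Two inconsistencies in the protocol do not remove the problem. Sections 3 and 9.1 define the secondaries among hospitalized patients. That leaves the chance of an empty arm unchanged and would fit the same model to about 33 patients. Section 9.2 refers to a primary Kaplan-Meier analysis. If that governed, the problem would take another form, but section 9.4.2 specifies the logistic model. The unadjusted log-rank tests in section 9.4.9 remain computable with an empty arm, but they are exploratory.

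**Conclusion.** The point holds as a gap in the secondary analysis. A confirmatory, Holm-tested analysis is tied to a model with fewer than 3 expected events per slope for f up to 50%, and to an estimand that has no finite value when the resveratrol arm has no events. That chance runs from about 38% to 0.8% as f goes from 10% to 50%, and is higher if resveratrol lowers hospitalization below 10%.

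That an empty arm gives an infinite coefficient is certain; how often it happens rests on the assumed f. The practical loss is modest: at most about 5% of trials over the values of f examined would forfeit a Firth result significant at 2.5%, and only if a Wald test or standard pooling is used. The primary analysis is not affected by this point. It is a cheap improvement, best made before unblinding.

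**What to change.** In section 9.4.3, replace the sentence that carries over the primary procedure with a rule for the secondary endpoints:

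1. Firth-penalized logistic regression, with the treatment effect tested by penalized profile likelihood and a confidence interval from the same profile.
2. A pre-specified reduced covariate set, for example arm, age and risk group, to be used if events are sparse. State the trigger in advance, for instance as a number of events pooled over both arms.
3. Missing outcomes: use the same penalized model for the imputation and state how results are combined, or take observed outcomes as the main secondary analysis. Keep the tipping-point analysis as sensitivity. It cannot replace the main analysis, because it gives a range of results and Holm needs one p-value per endpoint.

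The cost is a few sentences in the SAP and less covariate adjustment in the secondaries: sex, race and ethnicity would drop out when the reduced set applies. Sample size and data collection do not change.

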9.4.4 SAFETY ANALYSES

Adverse events will be coded according to the Common Terminology Criteria for Adverse Events (CTCAE), and each AE will be counted at most once per participant. Severity, frequency, and relationship of AEs to the study intervention will be presented by System Organ Class and preferred term groupings. Start date, stop date, severity, relationship, expectedness, outcome, and duration will be reported for each AE. Adverse events leading to premature discontinuation from the study intervention and serious treatment-emergent AEs will be tabulated. The safety population will be used for safety analyses.

9.4.5 BASELINE DESCRIPTIVE STATISTICS

Intervention groups will be compared on baseline characteristics, including demographics and baseline risk factors. Sample proportions, means and standard errors, or medians and ranges will be provided as appropriate for each distribution. No inferential statistics will be used. Descriptive statistics will be reported for the intention-to-treat population.

9.4.6 PLANNED INTERIM ANALYSES

An independent DSMB will monitor safety data on a continual basis throughout the trial. One interim analysis will be carried out after the first 100 patients have completed the initial 21-day study period. After 100 patients have been randomized, enrollment will pause until all randomized patients have completed at least 21 days of follow-up to evaluate the primary endpoint and the interim analysis has been completed. The DSMB can recommend enrollment suspension or study termination for reasons of safety. Study enrollment will be suspended by the PI when (1) any subject experiences a Grade 3 or higher adverse event toxicity (defined in 8.3.3.1) that is probably, or definitely related to the study agent, or when (2) stopping is indicated by the statistical stopping rule defined below. An enrollment suspension under either scenario will trigger an ad hoc safety review by the DSMB. Following DSMB review and recommendation, the IRB and FDA will determine whether study enrollment will resume.

The interim and final analyses will use the Hwang-Shih-DeCani alpha spending function with parameter gamma = -4 (O'Brien-Fleming–like) for the upper (superiority) bound under the null hypothesis with total one-sided Type I error 2.5%, and for the lower (safety or futility) bound under the alternative hypothesis with total Type II error 20% (80% power). Under the assumption of a binding futility bound and a placebo arm hospitalization rate of 25%, the probability of declaring futility at the interim analysis is 3% if the resveratrol arm hospitalization rate is 10% (alternative hypothesis), 55% if the resveratrol arm hospitalization rate is 25% (null hypothesis), and 75% if the resveratrol arm hospitalization rate is 30%. The R package gsDesign will be used to determine stopping boundaries.

9.4.7 SUB-GROUP ANALYSES

Stratified versions of the primary and secondary efficacy endpoint analyses will constitute exploratory subgroup analyses, with each variable analyzed separately. Variables defining strata are as follows.

- Age (65 or older versus 64 or younger)
- Sex
- Race
- Ethnicity
- Presence of at least one factor indicating membership in a high-risk group:
 - Blood disorder, including sickle cell disease or taking blood thinners.
 - Chronic kidney disease.
 - Chronic liver disease.
 - Compromised immune system (e.g., on chemotherapy, high dose steroids, immunosuppressant medications, HIV/AIDS).
 - Heart disease.
 - Lung disease.
 - Neurologic disease.
- ACE inhibitor / ACE Receptor Blocker (ARB) use.

Age is included due to known association with risk of complications due to COVID-19. Sex, race, and ethnicity are included in compliance with the NIH policy on the Inclusion of Women and Minorities as Participants in Research Involving Human Subjects. Comorbidity and concomitant medication risk factors are combined to limit the multiplicity of comparisons.

A formal multiplicity-corrected subgroup analysis procedure will be carried out via credible subgroups (Schnell, 2016). A logistic regression model will be fit with age and presence of at least one factor indicating membership in a high-risk group, their interactions with study arm, and study arm alone. Bounds for the benefiting subpopulation of patients, defined by age (as a continuous variable) and risk category will be computed at the 80% credible level.

9.4.8 TABULATION OF INDIVIDUAL PARTICIPANT DATA Individual participant data will not be presented.

. . . .

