9.4 STATISTICAL ANALYSES

9.4.1 GENERAL APPROACH

Uncensored data will be summarized by percentages, means and standard deviations, or medians and ranges as appropriate for each variable's distribution. Data subject to censoring (e.g., hospitalization) will be summarized by Kaplan-Meier estimate.

Unless otherwise noted, all hypothesis tests will be two-sided and at the 5% significance level. Similarly, confidence intervals will be two-sided and at the 95% confidence level. Declarations of superiority will be declared if the corresponding hypothesis test is significant and the direction of the estimated treatment effect is favorable to resveratrol.

In addition to local hypothesis tests, we will use a multiple testing procedure to control the familywise Type I error at 5% for the primary and secondary endpoints together. The primary efficacy endpoint (hospitalization) will be tested at the 5% significance level; then, if the primary endpoint null hypothesis is rejected, the two secondary endpoints (ICU admission, invasive ventilation) will be tested via the Bonferroni-Holm procedure. No multiple testing adjustment will be made for exploratory or safety analyses.

Hospitalization, ICU admission, and invasive ventilation endpoints are composites that include death within 21 days of randomization.

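### Section 9.4.7 plans no treatment-by-factor interaction for sex, race, ethnicity or ACE inhibitor/ARB use, so the separate stratified analyses do not test whether the effect differs between levels

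*Combined protocol and SAP*

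**What the plan says.** Section 9.4.7 lists six stratifying variables: age, sex, race, ethnicity, high-risk group and ACE inhibitor/ARB use. For all six it says: "Stratified versions of the primary and secondary efficacy endpoint analyses will constitute exploratory subgroup analyses, with each variable analyzed separately".

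The same section then describes a formal credible-subgroups procedure at the 80% credible level: "A logistic regression model will be fit with age and presence of at least one factor indicating membership in a high-risk group, their interactions with" (here the sentence goes on to name the randomized treatment). That covers age and risk group. The other four variables are not in that model.

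No other section supplies a comparison between levels. The primary logistic model (9.4.2) and the Cox fits (9.4.9) list main effects only. ACE inhibitor/ARB use appears in neither.

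Section 9.4.1 sets the default for tests: "Unless otherwise noted, all hypothesis tests will be two-sided and at the 5% significance level". It sets confidence intervals at 95%, bases a superiority declaration on a significant result in the favorable direction, and makes no multiplicity adjustment for exploratory analyses.

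**The concern.** Each stratified analysis asks whether there is an effect within one level. The subgroup question is whether the effect differs between levels, and for four factors the plan has no estimate of that difference. A half-sized stratum has low power, so a common effect will often reach 5% in one level and miss it in the other by chance alone. A reader of the tables could take that pattern for effect modification.

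ACE inhibitor/ARB use deserves most attention. Sections 2.3.1 and 2.3.2 discuss ACE2 upregulation as possibly protective and possibly an aid to viral entry, so readers will look for a difference there.

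**Working it through.** **Inputs**
- Rates (9.2): "we require a 10% or lower hospitalization rate in the resveratrol arm, compared to a 25% rate in the placebo arm".
- Sample size (9.2): "complete follow-up on 95 subjects per arm with two-sample proportion test". This is 100 per arm less "5% non-informative loss to follow-up before 21 days".
- Test: two-sided 5% (9.2 and 9.4.1).
- Subgroup split: not given in the documents. Assumed to be two levels, split 50:50, with uneven splits as a range.

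**Formula.** With n per arm, d = p1 − p2 and pooled rate p̄ = (p1 + p2)/2:

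power = Φ[(d − 1.96·√(2p̄(1 − p̄)/n)) / √((p1(1 − p1) + p2(1 − p2))/n)]

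For weak effects the small opposite-tail term is added.

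**Step 1: the plan's own figure.** For p1 = 0.25, p2 = 0.10 and n = 95, p̄ = 0.175 and the two standard errors are 0.0551 and 0.0540. Power = Φ[(0.15 − 0.1081)/0.0540] = Φ(0.776) = 78.1%, within two points of the stated 80%. The odds ratio (0.10/0.90)/(0.25/0.75) = 1/3 also agrees with 9.2.

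**Step 2: one half of an even factor.** For n = 47.5 the standard errors are 0.0780 and 0.0764. Power = Φ[(0.15 − 0.1528)/0.0764] = Φ(−0.037) = 48.5%.

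**Step 3: discordance under an identical effect.** If the levels have power a and b, P(exactly one significant) = a(1 − b) + b(1 − a). For a = b = 0.485 this is 2 × 0.485 × 0.515 = 50%. Binomial simulation (200,000 trials) gave 49.7%.

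**Step 4: dependence on the true effect** (50:50 split, placebo 25%)

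| Resveratrol rate | Power per half | Exactly one half significant |
|---|---|---|
| 10% | 48.5% | 50% |
| 12.5% | 34.3% | 45% |
| 15% | 22.8% | 35% |
| 20% | 8.9% | 16% |
| 25% (no effect) | 5.0% | 9.5% |

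**Step 5: dependence on the split** (25% v 10%)

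| Split | Power, larger and smaller level | Exactly one significant |
|---|---|---|
| 60:40 | 56.0%, 40.4% | 51% |
| 70:30 | 62.7%, 31.6% | 55% |
| 80:20 | 68.5%, 22.5% | 60% |

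Lower placebo rates (assumed, same relative reduction, 50:50, simulated) reduce the figure: 44% at 15% v 6%, 36% at 10% v 4% and 17% at 5% v 2%.

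**Step 6: the alternative.** A Wald interaction test on the log odds ratio (0.5 added to each cell, two-sided 5%) was run in the same simulations. It found a false difference in 3.4% of trials at 25% v 10% with a 50:50 split, 2.6% with 80:20, and 4.6% with no effect and a 50:50 split.

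**Step 7: information available.** Expected events at the design rates are 95 × (0.25 + 0.10) = 33.25, so about 33 in all and about 17 in each half.

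Steps 1 to 6 use the unadjusted two-proportion test or a crude odds ratio. They do not reproduce the covariate-adjusted logistic model with multiple imputation, and they ignore interim stopping.

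**The case against.** The plan calls these analyses exploratory and never says that a result significant in one level and not in another will be taken as heterogeneity. A reader might infer that rule from the 5% default and the superiority rule in 9.4.1, but the documents do not state it. This stands: the discordance rate is the error of a possible misreading, not of a planned decision.

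A reader might also infer that only p-values will be available by level. That is not so. A stratified version of 9.4.2 gives the treatment coefficient in each level, with a 95% interval by default under 9.4.1, and for two levels a reader can form the contrast approximately. What is missing is the formal contrast itself.

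Next, the plan does have a formal tool for identifying who benefits: credible subgroups on age and risk group. Section 9.4.7 attributes the inclusion of sex, race and ethnicity to NIH policy. This largely stands, and it makes selection of patients for a later trial on those factors speculative. It does not cover ACE inhibitor/ARB use, the one factor of the four with a mechanistic rationale in the protocol.

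Finally, it is tempting to say that false contrasts are nearly certain across four factors, using 1 − 0.5⁴ = 94%. That assumes four independent events, but the factors re-split the same 190 outcomes. Simulating four independent even factors gives about 80% at 25% v 10%, 63% at 25% v 15% and about 25% with no effect.

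On the other side, the exploratory label limits the strength of a claim but does not supply the comparison. Conditioning on a significant overall result, when subgroup tables attract most attention, raises the 50:50 figure to 57% at 25% v 10% and about 65% at 25% v 15% (simulated).

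**Conclusion.** The gap is real and small. For sex, race, ethnicity and ACE inhibitor/ARB use the plan has no analysis of whether the treatment effect differs between levels.

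The figure of about 50% rests on three conditions: a true effect near 25% v 10%, a two-level factor split about evenly, and a reader who compares significance across levels. The first is the difference that 9.2 requires for 80% power, not a prediction. The second is our assumption, and race may have more than two levels. The third is not written in the plan. A uniform effect therefore does not always look different half the time: with no effect anywhere the figure is about 10%.

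No primary, secondary or formal subgroup conclusion changes. This is a minor improvement to exploratory reporting.

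**What to change.** In 9.4.7, for each of sex, race, ethnicity and ACE inhibitor/ARB use, specify one logistic model in all ITT participants. It should contain the 9.4.2 covariates, the factor (a new term only for ACE inhibitor/ARB use) and arm-by-factor. Report the interaction estimate with its 95% confidence interval, and take level-specific effects with intervals from the same model. Add a sentence that differences in within-level significance will not be read as heterogeneity. Within-level p-values need not be banned.

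The cost is SAP wording and minor programming. The interaction estimates will be imprecise with about 33 expected events, and sparse levels of race or ethnicity may have to be combined. The plan should say both in advance.
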